PROTOCOL and SAP

The Role of Human Fibrinogen Concentrate (RiaSTAP) in Decreasing Blood Loss and the Need for Component Blood Therapy in Infants Undergoing Cardiopulmonary Bypass

National Clinical Trial (NCT) Identification Number: NCT02822599

December 7, 2017

Purpose of Study

The goal of the study is to determine whether the use of Human Fibrinogen Concentrate (RiaSTAP) will decrease blood loss and the need for component blood therapy in neonates and infants undergoing cardiopulmonary bypass. RiaSTAP will be administered after termination of Cardiopulmonary Bypass (CPB) at a dose of 70 mg/kg, in a prospective, randomized, controlled study. We hypothesize that the administration of RiaSTAP in this manner will reduce peri-operative bleeding and transfusion requirements.

Background

Severe postoperative bleeding is a serious complication after cardiac surgery and results in increased morbidity and mortality¹². The bleeding is often multifactorial and influenced by both surgical factors and impaired hemostasis. The impaired hemostasis after cardiac surgery may be caused by enhanced fibrinolysis, platelet (PLT) dysfunction and coagulopathy secondary to the exposure of blood to artificial surfaces, and the surgical trauma³.

In children less than 12 months old with congenital heart disease, bleeding after cardiac surgery is further complicated as the fibrinogen of these patients is qualitatively dysfunctional⁴. Moreover, the coagulation systems of neonates and children undergoing CPB are profoundly affected by hemodilution⁵ and by consumption⁶. As a result, neonates and young infants undergoing complex cardiac repairs often receive multiple units of blood products, both in the operating room (OR) and intensive care unit (ICU).

Preoperative fibrinogen concentration is an independent predictor of post-operative bleeding volume. Fibrinogen concentration, even when within the normal range, is a limiting factor for post-operative hemorrhage⁷. The prophylactic infusion of fibrinogen concentrate has been shown to reduce bleeding after coronary artery bypass graft (CABG) surgery without evidence of hypercoagulability⁸. Moreover, ROTEM FIBTEM test guided fibrinogen concentrate administration was associated with reduced transfusion requirements and 24 hour postoperative bleeding in patients undergoing aortic valve operations and ascending aortic reconstructions⁹.

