Both Groups will receive the normal standard of care both before and especially after this event. This will be the only event that is different for the two groups. To avoid selection bias, the Pharmacy will perform the randomization using Research Randomizer. Briefly, for each patient, a randomly generated integer between 1-30 will be produced. If the number is even, the patient will be assigned to Group 1. If the number is odd, the patient will be assigned to Group 2. The randomization process and schedule will be provided by the Principal Investigator's office, but the actual patient assignment will be done by Pharmacy.

All operating room and ICU personnel will be blinded to the patient's Group assignment. The only persons who will have access to the identity of the Group assignment from the time of randomization until 24 hours after surgery will be members of the Pharmacy staff. NONE of these individuals will be involved in patient care. The DSMB will be unblinded AFTER the study treatment period concludes (24 hours after surgery).

Endpoints:

Primary efficacy endpoints will be estimated as follows:

- postoperative bleeding (EBL) during the first 24 hours (hr) after surgery (cc/kg),
- the identity and total volume of transfused blood products (cc/kg) given in the peri-operative period, separated out into its components,
- hemoglobin concentration 2 hr. and 24 hr. after surgery and
- effects of fibrinogen infusion on global hemostasis 2 hr. and 24 hr. after surgery (PT, PTT, INR, fibrinogen level, platelet count and ROTEM analysis).

Post-operative period begins after the patient leaves the operating room. The need for Factor VII use and dose will also be included as a primary end point. Factor VII is typically used only if there is profuse bleeding not amenable to component transfusion therapy.

Secondary end points will include:

- the number of post-op hours requiring ventilator support,
- Length of Stay (LOSH) in the hospital,
- Length of Stay (LOS ICU) in the Cardiac Intensive Care Unit (CICU) and
- the need for re-exploration for bleeding within the first 12 hours.

The primary safety endpoints that will be monitored are the presence of a clinical adverse events. Clinical adverse events (AEs) are defined as any clinical signs of central or peripheral thromboembolism, respiratory or circulatory failure, or allergic reactions during hospital stay. It will also include infection with a blood-borne pathogen.

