PRBC: Volume required = Blood volume (V) x desired Hct increase / Hct of red cell unit (70%)

FFP: 20 cc/kg

Plateletpheresis: 20 cc/kg

Cryoprecipitate: 10 cc/kg

The ROTEM analysis algorithm is below (Figure 4).

Four main scenarios based on clinical observation and TEM results were possible:

1. Insignificant bleeding—normal TEM \Rightarrow no transfusions
2. Insignificant bleeding—abnormal TEM \Rightarrow no transfusions
3. Significant bleeding—normal TEM \Rightarrow surgical reevaluation
4. Significant bleeding—abnormal TEM \Rightarrow transfusion of blood products as indicated by:
 - a. fib-TEM MCF < 7 mm \Rightarrow cryoprecipitate
 - b. hep-TEM MCF < 50 mm \Rightarrow platelets,
 - c. hep-TEM CT > 240 seconds \Rightarrow FFP,
 - d. hep-TEM CFT > 110 seconds \Rightarrow cryoprecipitate and /or platelets depending on MCF

If clinically indicated (continuing bleeding) or to verify the treatment effect and control heparin reversal, a second set of in-TEM, hep-TEM, and fib-TEM analyses will also be performed during wound closure. ACT will be tested in all patients to control for heparin reversal. If patients have both a pathological ACT and TEM, protamine will be administered.

Postoperative bleeding in the ICU will be defined as the total amount of chest tube drainage after closure of the sternum and during the first 24 postoperative hours. If the sternum is not closed, it will be defined as the total chest tube drainage during the first 24 postoperative hours. An intensive care nurse blinded to group assignment will record the bleeding every hour. The amount of transfused red blood cells (RBC), FFP, cryoprecipitate and platelets during the hospital stay will be recorded in cc/kg. The transfusion triggers will be as described above. The CICU physicians and nurses will not be informed of the preoperative fibrinogen concentration or group assignment.

Patient Assessment:

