Primary efficacy endpoints will be postoperative bleeding during the first 24 hours (hr) after surgery (cc/kg), the total volume and identity of transfused blood products (cc/kg), hemoglobin concentration 2 hr. and 24 hr. after surgery and effects of fibrinogen infusion on global hemostasis 2 hr. and 24 hr. after surgery (PT, PTT, INR, fibrinogen level, platelet count and ROTEM analysis). Secondary end points will include the number of post-op hours requiring ventilator support, Length of Stay (LOS) in the Cardiac Intensive Care Unit (CICU), the need for re-exploration for bleeding within the first 12 hours, and LOS in the hospital. The need for Factor VII use and dose will also be included.

The primary safety endpoint is a clinical adverse event. Clinical adverse events are defined as:

1. Any clinical signs of central or peripheral thromboembolism. This will then be confirmed by Doppler ultrasound. Assessments will be made once per shift (once every eight hours)
2. Respiratory or circulatory failure. Parameters of respiration, like respiratory rate (RR), end-tidal CO₂ (ETCO₂) and circulation, like heart rate (HR), rhythm, blood pressure (BP), arterial oxygen saturation (SpO₂) are monitored continuously while in the ICU. Respiratory failure will be defined as the need for reintubation after extubation. Circulatory failure will be defined as cardiac arrest.
3. Allergic reactions during hospital stay. These will include signs or symptoms like urticaria, wheezing, angioneurotic edema, and anaphylaxis.
4. Infection with a blood borne pathogen. Manifestation of an infection with a blood borne pathogen is unlikely to occur during the study treatment period, which ends 24 hours after the end of surgery. If this were to occur, it would not manifest itself for weeks or even months.

Patients will be assessed once per shift (once every eight hours) for signs of thromboembolism. Any evidence of thromboembolism will warrant a vascular ultrasound to assess the integrity of the vessel.

Adverse events will be monitored until discharge.

All patients will be assessed for signs and symptoms of thromboembolism, per routine care. Specifically, patients will be assessed for signs and symptoms of central and arterial

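### Respiratory failure is scored as any reintubation after extubation, so an already-extubated infant reintubated only for surgery or another procedure counts as a primary safety event

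*Combined protocol and SAP*

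**What the plan says.** In the combined protocol and SAP, the Patient Assessment section says "The primary safety endpoint is a clinical adverse event" and lists four kinds. Item 2 is respiratory or circulatory failure. It opens with continuously monitored signs such as respiratory rate, end-tidal CO2 and oxygen saturation, and then gives one scoring rule for the respiratory part: "Respiratory failure will be defined as the need for reintubation after extubation". Circulatory failure is scored as cardiac arrest only. On the window, the section says "Adverse events will be monitored until discharge".

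The Endpoints section, Table 1, the Schedule of Events and its footnotes add no limit on cause, no exclusion for a planned or surgical intubation, and no item for the reason. The paragraph before Stopping Criteria has the Safety Team (the intensive care physicians) evaluate each event and says that they are no longer blinded after 24 hours. It gives no criteria for attributing a reintubation.

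Return to surgery is foreseen. The secondary endpoints include "the need for re-exploration for bleeding within the first 12 hours", and the ROTEM algorithm under Drug protocol sends "Significant bleeding—normal TEM" to surgical reevaluation. Ventilation is recorded as "the number of post-op hours requiring ventilator support", with no expected time of extubation.

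**The concern.** The signs that introduce item 2 show that failure of breathing is meant. The rule counts something wider. Three infants illustrate it:

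- One is extubated at 6 hours and reintubated at 10 hours for bleeding re-exploration, with normal lungs. The rule scores respiratory failure, and the same episode is already a secondary endpoint.
- One is extubated on day 2 and intubated on day 9 for an unrelated procedure. The rule scores respiratory failure.
- One is reintubated for hypoxia. The rule scores respiratory failure, correctly.

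The first two are miscounts. With 15 infants planned per group, the respiratory count will be a handful at most, so one or two such records can blur or hide a real difference. Reporting the components of the safety endpoint separately does not help, because the miscount lies inside the component.

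**Working it through.** **No plan figure to reproduce.** The documents state 30 infants, 15 per group, with no power, effect size or event rates. The check therefore has two parts: the wording, set out above, and an illustration of size under assumed rates.

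**Inputs from the documents.** 15 per group (Randomization); Fisher's exact test for categorical variables and significance at p ≤ 0.05 (Statistical Analyses). The test's sidedness is not stated, so I take it as two-sided. I take the respiratory component on its own.

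**Assumed inputs, none from the documents.**
- Re-exploration q: 5% on RiaSTAP, 15% on control.
- Share s of re-explored infants already extubated: 0, 25, 50 or 100%. Only these infants can be reintubated and so miscounted.
- True respiratory failure r: either 10% in both arms, or a harm of 30% on RiaSTAP v 5% on control.
- Re-exploration and true respiratory failure are independent.

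**Formulas.** Scored rate = 1 − (1 − r)(1 − s·q).

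With r = 10% in both arms, spurious control excess = 15 × (1 − r) × s × (q control − q RiaSTAP) = 15 × 0.90 × s × 0.10 = 1.35·s infants.

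At s = 100%: control 1 − 0.90 × 0.85 = 0.235; RiaSTAP 1 − 0.90 × 0.95 = 0.145; 15 × 0.09 = 1.35.

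Power is the exact probability of a significant Fisher result with RiaSTAP higher, enumerated over two binomials of size 15.

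| Already extubated | Scored, true 10% v 10% (RiaSTAP v control) | Spurious control excess, infants of 15 | Scored, true 30% v 5% | Power |
|---|---|---|---|---|
| 0% | 10.0% v 10.0% | 0 | 30.0% v 5.0% | 0.275 |
| 25% | 11.1% v 13.4% | 0.34 | 30.9% v 8.6% | 0.194 |
| 50% | 12.25% v 16.75% | 0.675 | 31.75% v 12.1% | 0.135 |
| 100% | 14.5% v 23.5% | 1.35 | 33.5% v 19.25% | 0.065 |

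**Dilution without any arm difference.** If procedural reintubation is 15% in both arms, the 30% v 5% harm is scored as 1 − 0.70 × 0.85 = 40.5% v 1 − 0.95 × 0.85 = 19.25%. The difference shrinks from 25 to 21.25 points and power falls from 0.275 to 0.127.

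**Direction.** The excess carries the sign of q control − q RiaSTAP. Swap the two assumed rates and the same 1.35·s infants are added to RiaSTAP.

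**One record.** Five events v none gives p = 0.042. One procedural reintubation added to the other arm makes it five v one, p = 0.169.

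**Spurious significance.** Procedural records alone would need to be 5 v 0 to reach significance (4 v 0 gives p = 0.0996). In the 14.5% v 23.5% scenario, a significant result favouring RiaSTAP has probability about 0.036.

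**The case against.** A reader might infer that the rule makes RiaSTAP look safer for the lungs. The documents do not support that. The hypothesis reads "We hypothesize that the administration of RiaSTAP in this manner will reduce peri-operative bleeding and transfusion requirements"; it does not mention re-exploration. The algorithm sends significant bleeding to surgical reevaluation when the TEM is normal, and to blood products when it is abnormal. A bleeding infant whose TEM RiaSTAP has corrected would take the surgical branch, while a control with low fibrinogen would be transfused. Re-exploration could be equal between arms, or more frequent on RiaSTAP. This objection stands, and I make no claim about direction.

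A reader might also infer that any bleeding difference turns into a respiratory-safety difference. It does not. Drainage and transfusion do not enter this component, and an infant re-explored while still ventilated is not reintubated. The algorithm also operates in the operating room, before any extubation. This is why the table runs over the share already extubated and starts at no effect.

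Little turns on the result. Power for a 25-point harm is only 0.275 even with a clean count, and the Stopping Criteria concern thromboembolism alone. Both are true and keep the point minor. Safety data are nevertheless reviewed after 10, 20 and 30 subjects, and the count will be reported.

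Finally, the case can partly be recognised from what is collected: re-exploration within 12 hours and ventilation duration are recorded, and the Safety Team looks at each event. That covers early bleeding re-exploration only. Later returns and other procedures have no listed item, and sorting them without a written rule would fall to physicians who know the assignment after 24 hours. One could also read the word need in the definition as respiratory need, but the text does not say so.

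**Conclusion.** The point holds as a flaw of definition: the written rule counts reintubations done only for a procedure as respiratory failure, within the primary safety endpoint. Under the assumed 5% v 15% re-exploration, the distortion is 0 to 1.35 infants of 15 with equal true failure, and power for a 30% v 5% harm lies between 0.275 (no distortion) and 0.065. The size depends entirely on assumed rates and on how many infants are extubated before they return to surgery, which the documents do not give. The realistic risk is dilution or distortion of a very small count, in either direction. A false significant difference is unlikely. Severity: minor.

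**What to change.** In Patient Assessment, item 2, add that a reintubation done solely to provide anesthesia for a documented return to the operating room, catheterization or other procedure does not count as respiratory failure, and that every other reintubation still counts. Re-exploration for bleeding stays in its own endpoint.

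Keep the exclusion that narrow. Limiting the event to respiratory or airway causes would drop reintubation for circulatory or neurological deterioration, which might then be scored nowhere, since circulatory failure is cardiac arrest only. It would also require far more judgement about cause.

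Record the reason for each reintubation, have it classified by someone without access to the assignment, list procedural reintubations separately, and report the component with and without them.

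The cost is one sentence and one field on the form. The downside is a small classification judgement for a few infants. It must be made blind, because the Safety Team is unblinded after 24 hours. The change affects how events are counted and leaves clinical care as it is.

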Patients under 10 kg in body weight will have the CPB pump primed with one unit of Packed Red Blood Cells (PRBC) and 200 cc Fresh Frozen Plasma (FFP). In patients over 10 kg a pure crystalloid prime will be used. Target hemoglobin (Hg) while on CPB will be 9 gm/dL, but the transfusion trigger for additional units of PRBC will be 7 gm/dL.

Drug protocol:

The following laboratory studies will be obtained prior to surgery: Complete Blood Count (CBC), Prothrombin time (PT), International Normalized Ratio (INR), Partial Thromboplastin time (PTT), Platelet count, and a Fibrinogen level; an electrolyte profile will also be done. An Activated Clotting Time (ACT) and a Thromboelastometry analysis [REDACTED], a device that assesses the viscoelasticity of whole blood and other parameters, will be done after an A-line is placed (Figure 1).

A blood products transfusion algorithm was developed based on four previous studies published in the literature, modified for pediatrics¹⁶¹⁷¹⁸¹⁹ (Figure 2). Blood is measured in the cell saver reservoir and the suction canister every fifteen minutes while in the OR. Clinically significant bleeding, requiring treatment, will be defined as a rate in excess of 10 cc/kg/hr calculated every 15 minutes while in the OR. Calculations will be done every 60 minutes in the CICU.

After rewarming, but prior to the termination of CPB a ROTEM analysis will be done. Platelets or FFP will be administered at this time, while still on CPB, if the ROTEM results indicate a deficiency of either component. Then immediately after the termination of CPB, RiaSTAP or NS will be administered depending on the group assignment. Then, as per routine care, a ROTEM analysis and fibrinogen level will be assessed and the transfusion algorithm will be continued. *If the ROTEM indicates a fibrinogen deficiency, cryoprecipitate will be given.* Thereafter, as per routine care, a ROTEM analysis will be done at least every 30 minutes while in the OR or sooner at the discretion of the OR team. Once the patient leaves the OR a ROTEM will be done at least every 60 minutes for the first six hours or until clinically significant bleeding has stopped, whichever comes first; ROTEMs can be done more frequently at the discretion of the ICU staff caring for the patient. The blood products transfused after separation from CPB will be based on the protocol below (Figure 3). Dosing amounts of the required component therapy will be based on the formula below:

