line thrombosis. These include edema, leg pain and tenderness, erythema, and discoloration for venous thrombosis, as well as loss of distal peripheral pulses, pain, pallor, paresis, paresthesias, decreased skin temperature for arterial thrombosis. If any of these signs and symptoms appear, Doppler Ultrasound examinations of the affected area will be performed.

The Safety Team, which consists of the Cardiac Intensive Care Unit physicians, will evaluate each event when it occurs; they will not be blinded to patient assignment after 24 hours. Please see safety assessments and timing below. These represent minimums as prescribed by the protocol. Assessments may be more frequent (See table 1).

Stopping Criteria:

A statistically significant increase in thromboembolic phenomenon between Group 1 and Group 2 will trigger a stop in enrollment. This will be monitored by the Safety Team.

Table 1: Assessments

Assessment	Timing in OR	Timing in ICU
EBL	q 15 min	hourly
ROTEM	q 30 min as needed	hours 2 and 24, or as needed hourly until bleeding ceases
peripheral thromboembolism	N/A	q8 hrs, or as needed
hemoglobin	as needed	hours 2 and 24
PT/PTT, platelets, fibrinogen	prior to surgery if not previously done	hours 2 and 24

Schedule of Events

	Pre-Operative	Intraoperative	2 hours Post-Operative	24 hours Post-Operative	When occurs	60 ± 14 days
Informed Consent/Assent	x					
Eligibility Assessment	x					

Demographic Data	X					
Medical History	X					
Baseline Assessment ¹	X					
Body Weight and Height	X					
Concomitant Medications ⁴	X	X				
Randomization		X				
Administration of Study Drug		X				
Pharmacy Prep of Study Drug		X				
Laboratory Studies ²	X		X	X		
Adverse Events		X	X	X	X	X
Surgical and Cardiopulmonary Bypass Data ³		X				
Estimated Blood loss (EBL) ^{5,6}					→	
ROTEM Analysis ^{9,11}	X	X ^{7,10}	X	X	X ⁸	
Identification of total transfused blood products ¹²				X		
Thromboembolic Assessment ¹³			→		X	
Factor VII					X	
Length of Stay ICU and Hospital					X	
Mechanical ventilation duration					X	
Need for Re-exploration first 12 hours			X	X		
Phone assessment						X

1. Assessment includes allergies, diagnosis, procedure(s)
2. Laboratory collection and assessment includes CBC, prothrombin time (PT), international normalized ratio (INR), partial thromboplastin time (PTT), fibrinogen level. Pre-Operative includes complete platelet count, and electrolyte profile.

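### The treating CICU physicians are unblinded at 24 hours, while judgement-dependent outcomes can still accrue, and they also hold the between-group stopping comparison

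*Combined protocol and SAP*

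**What the plan says.** **Statements that end the blind at 24 hours.**
- Patient Assessment: the Safety Team, made up of the CICU physicians, "will evaluate each event when it occurs; they will not be blinded to patient assignment after 24 hours".
- Randomization: the only people with access to the assignment "from the time of randomization until 24 hours after surgery will be members of the Pharmacy staff", and "NONE of these individuals will be involved in patient care". The same paragraph adds: "The DSMB will be unblinded AFTER the study treatment period concludes (24 hours after surgery".
- Methods to Minimize Bias: one sentence ties the practitioners' blind to the study treatment period, which ends 24 hours after surgery.

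**Statements with no end time.**
- Drug protocol: "The CICU physicians and nurses will not be informed of the preoperative fibrinogen concentration or group assignment".
- Randomization and Methods to Minimize Bias: each has a sentence saying that all operating room and ICU personnel are blinded.

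**Stopping comparison.** Under Stopping Criteria, a statistically significant excess of thromboembolism between the groups halts enrolment, and the Safety Team monitors this. No passage gives the DSMB this task. Safety Monitoring sets data reviews at 10, 20 and 30 subjects without naming who performs them.

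**Outcomes with no 24-hour limit.** The secondary endpoints include "the number of post-op hours requiring ventilator support", CICU stay and hospital stay. Factor VII need and dose is called a primary end point under Endpoints, and the Schedule of Events marks it for recording whenever it occurs. The primary safety endpoint covers clinical signs of thromboembolism, allergic reactions over the hospital stay, and respiratory failure: "Respiratory failure will be defined as the need for reintubation after extubation". Adverse events are followed to discharge, and a telephone call at 60 ± 14 days asks about further events.

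**The concern.** Extubation, reintubation, transfer out of the CICU, giving Factor VII, and noting an early sign of thrombosis or allergy all involve clinical judgement. A physician who knows the arm may make these decisions differently, without intending to. The affected comparisons would then mix a drug effect with an effect of knowing the treatment.

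The stopping rule adds to this. After 24 hours the same physicians would treat the child, evaluate each event and compare the arms, all with knowledge of assignment. With 15 patients planned per arm, a few events recognised or missed differently could change that comparison. An unblinded running comparison held by the treating team could also colour the care of later patients.

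Two stated safeguards do not reach this problem. Doppler confirmation limits false-positive thromboembolism, but it is ordered only after a sign has been noticed. The blinded, independent biostatistician works on recorded data and cannot undo bedside decisions.

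**Working it through.** The plan gives no figure to reproduce here: no SD, expected duration, event rate or power. The check is therefore mainly a comparison of passages.

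**Step 1. Does the plan unblind the treating physicians?** The Safety Team sentence says so directly. The Pharmacy-only access window and the treatment-period sentence in Methods to Minimize Bias also stop at 24 hours. The Drug protocol sentence and the two all-personnel sentences have no limit. They may simply lack a time qualifier, but the text does not say so. What follows holds if the Safety Team sentence governs.

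**Step 2. Which outcomes can still accrue after 24 hours?**

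| Outcome | Role in the plan | Exposed after 24 h? |
|---|---|---|
| Chest-tube bleeding to 24 h | Primary | No |
| Hemoglobin, coagulation tests and ROTEM at 2 h and 24 h | Primary | No; the last is at the boundary |
| Factor VII need and dose | Primary (Endpoints) | Yes, no cap |
| Transfusion volume | Primary | Only if the hospital-stay window in Drug protocol applies; Endpoints says peri-operative and the Schedule marks 24 h |
| Ventilator hours | Secondary | Only in children still ventilated, or reintubated, after 24 h |
| CICU stay | Secondary | Yes |
| Hospital stay | Secondary | As far as CICU physicians influence it |
| Re-exploration within 12 h | Secondary | No |
| Thromboembolism recognition, reintubation, allergic reactions | Primary safety | Yes, for events after 24 h |

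**Step 3. What could a bias do? (Illustration only.)** Inputs from the plan: 15 per arm (Randomization), Student's t-test and a 0.05 threshold (Statistical Analyses). Assumptions: two-sided test (the plan does not state sidedness), normal outcomes, equal variances, equal arms, no true drug effect, and a knowledge-driven shift of d SD between the arm means.

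- Degrees of freedom = 15 + 15 − 2 = 28; critical t = 2.048.
- Noncentrality = d × √(15/2) = d × 2.739.
- P(reject) = P(|T| > 2.048), where T is noncentral t with 28 df.

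| Assumed shift d | Noncentrality | P(reject) |
|---|---|---|
| 0 | 0 | 5.0% |
| 0.1 SD | 0.274 | 5.8% |
| 0.25 SD | 0.685 | 10.1% |
| 0.5 SD | 1.369 | 26.2% |

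The shift here is an average over all patients. If only half were exposed (also an assumption), a 0.25 SD effect among them averages 0.125 SD, and P(reject) is 6.3% rather than 10.1%. A shift against the drug would instead hide a real benefit.

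**The case against.** **ROTEM already gives the arm away.** Methods to Minimize Bias concedes that ROTEM values may reveal the study drug, and in the ICU "ROTEMs can be done more frequently at the discretion of the ICU staff caring for the patient". Fibrinogen is also measured at 2 h and 24 h. This stands in part, and it is why the added bias may be modest. But possible inference by some physicians is not the same as planned disclosure to all of them.

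**Exposure is partly inferred.** No passage says that CICU physicians decide discharge once a child has left the CICU, or that physicians rather than nurses make the eight-hourly thromboembolism check. The documents give no ventilation times. This stands, and the table in the working is limited accordingly. A reader might infer that three of the four secondary endpoints are wholly compromised. The documents do not support that.

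**The Drug protocol sentence may govern.** If so, CICU staff never learn the arm, and what remains is a contradiction to reconcile. That is possible, though three statements elsewhere point to 24 hours.

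**The shifts are invented.** They are, and the table would fit any 15 v 15 comparison. It shows sensitivity and estimates nothing about this trial.

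**Safety needs unblinding.** The plan gives no reason why these physicians need the assignment after 24 hours. Before then, it expects blinded CICU staff to detect thromboembolic events and intervene with routine care.

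**Conclusion.** The concern holds within limits. As written, the plan ends the blind of the treating physicians while several judgement-dependent outcomes can still accrue, and it makes the same physicians the monitors of the between-group stopping comparison although a DSMB exists. This rests on the Safety Team sentence taking precedence over the unlimited sentence in Drug protocol. If it does not, the defect is an unreconciled contradiction together with a misplaced stopping duty.

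A reader might infer that the main efficacy result is compromised. The documents do not support that: 24-hour bleeding and the 2 h and 24 h laboratory measures are complete when the blind ends. Among the primary efficacy measures, only Factor VII use, and transfusion if counted over the hospital stay, can run past that point. Endpoints describes Factor VII as typically reserved for profuse bleeding, and the plan does not say how often it is given after 24 hours.

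Nor do the documents show that bias will occur, how large it would be, or which arm it would favour. The rates of 5.8%, 10.1% and 26.2% depend entirely on the assumed shifts. The point should be fixed because the remedy is cheap and the exposure avoidable.

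**What to change.** 1. **Patient Assessment.** Delete the clause that ends the Safety Team's blind at 24 hours.
2. **One end to the blind, stated in Randomization, Drug protocol, Patient Assessment and Methods to Minimize Bias.** CICU physicians, nurses and all other treating or assessing staff, including whoever makes the 60-day call, stay blinded until the last patient's follow-up is complete and the data are locked. Lifting the blind patient by patient at discharge would not be enough. While enrolment continued, the same physicians could build a running tally by arm, and the 60-day call would be made unblinded.
3. **Access.** Only Pharmacy and, after 24 hours, the DSMB hold the assignment. Extend the existing bar on involvement in patient care to both.
4. **Stopping Criteria.** Replace the sentence that gives monitoring to the Safety Team: the Safety Team evaluates and reports each event blinded, and the DSMB makes the between-group comparison.
5. **Emergency unblinding.** Allow it for a single patient through Pharmacy, logged and reported.

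The cost is wording changes and one written DSMB duty, with no added patients, visits or tests. The downsides are that clinicians must request the assignment when they need it, and that the blind stays partial because ROTEM and fibrinogen results may reveal the arm.
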